Clinical outcomes will be monitored periodically as per standard of care with regular and appropriate laboratory and clinically reported events. For those taking SGLT2i, we expect DKA ~0.2%, hypoglycemia ~3%, UTI, and/or mycotic infections at a rate of ~6% and will prospectively collect and monitor clinical data related to this program. We will also review the EHR for hospitalizations. GLP1-RA are known to cause gastrointestinal side effects in ~20% of users; these are mitigated by slow titration. More serious AEs such as gallbladder events are rarer and occur at a frequency lower than may be observed in a sample of this size. The details of the management protocol, including monitoring for safety, will be based on existing guidelines. This will be submitted separately to the P&T committee. HbA1c will be checked at 3 and 6 months after the initiation of therapy per ADA guidelines for usual care after diabetes medication change.

MONITORING AND QUALITY ASSURANCE

Describe the plan to be followed by the principal investigator/study staff to monitor and assure the validity and integrity of the data and adherence to the IRB-approved protocol. Specify who will be responsible for monitoring, and the planned frequency of monitoring. For example, specify who will review the accuracy and completeness of case report form entries, source documents, and informed consent.

NOTE: Regardless of monitoring plans by the sponsor or others, the principal investigator is ultimately responsible for ensuring that the study is conducted at his/her investigative site in accordance with the IRB-approved protocol, and applicable regulations and requirements of the IRB.

The study data will be monitored regularly by the principal investigator and clinical leads, supported by data analysts for quality assurance.

For guidance, refer to the following Partners policies:

 Data and Safety Monitoring Plans and Quality Assurance

<https://www.partners.org/Assets/Documents/Medical-Research/Clinical-Research/DSMP-in-Human-Subjects-Research.pdf>

 Reporting Unanticipated Problems (including Adverse Events)

<https://www.partners.org/Assets/Documents/Medical-Research/Clinical-Research/Reporting-Unanticipated-Problems-including-Adverse-Events.pdf>

PRIVACY AND CONFIDENTIALITY

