Primary Outcome: By design, no patients will be on SGLT2i or GLP-1 RA therapy at baseline. We are excluding patients who are on the drugs of interest at baseline, so our primary outcome is the proportion of prescription therapy provided at 6 months. Our null hypothesis is that with we would expect with our education only (control) arm to increase rate of prescription from 0% to 5% based on secular trends and from 0% to 20% increase in SGLT2i or GLP-1 RA therapy in our intervention group utilizing navigators. 100 patients per arm will allow a 25% dropout rate to maintain power > 80% to maintain an alpha level of 0.05. As we are comparing the timing of education in the A/B allocated groups, we expect that our sample size will provide ~80% power to detect an absolute rate of prescription difference of 15% between our immediate titration and education prior to titration groups (i.e., at 3 months)

Secondary Outcomes: With a mean HbA1c of 7.2% and a standard deviation of 1%, to obtain 80% power to detect a 0.5% difference in HbA1c, we would need to enroll 63 patients per arm (preliminary data.) To account for dropout, (expecting 25% dropout) we will calculate $N1 = n/(1 - \text{dropout rate}) \Rightarrow 63/0.75 = 84$ patients per arm.

Data Management

Mass General Brigham will create a data collection instance within the patient-management application. All data will be collected and stored within the Mass General Brigham firewall in a HIPAA-compliant, encrypted server, key variables data will be randomly sampled and verified for accuracy in 40 patients representing 20% of the study population. Data will be stored for at least 5 years after project completion.

Data Analysis

We will utilize SAS software, version 9.4 (SAS Institute) to conduct our statistical analysis.

There will be ongoing quality checks of the data. Before final analysis, the data will be queried for outliers and missing data. The primary analysis will not impute any missing data though sensitivity analysis may use imputation methods such as last observation carried forward (LOCF).

Definition of Analysis Sets

For the Full Analysis Set (FAS) Patients will be included all patients enrolled (intention-to-treat analysis.)

The Per protocol Set (PPS) will include patients that did not drop out or become unreachable and completed the entire quality improvement program.

Statistical Methods

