For our primary outcome, the percent of patients on either an SGLT2i or GLP-1 RA from baseline to conclusion of the study at 6 months post-enrolment, we will perform a Chi-Square test to determine a difference in the terminal rates at the end of the study to determine treatment effects between groups.

We will develop a cumulative incidence curve displaying patients both prescribed and taking DRIVE medications for the duration of the program.

We will perform t-tests and Fisher's exact test for the baseline univariate analysis. As we will be utilizing A/B allocation there should be no bias or confounding at baseline, however if any significant differences are found, we will correct for these utilizing logistic regression. A/B allocation with 200 patients should cause any confounders to balance between the groups. We will also perform a longitudinal model for binary outcome at 6 months. For our co-secondary outcomes, the change in the HbA1c, and PAM from baseline to the end of the 6-month study, these will be analysed with a paired t-test and we will report a mean and standard deviation. A secondary analysis will be to conduct linear regression models with two variables (baseline HbA1c and baseline weight) to control for any confounders.

We will conduct our analysis via the intention-to-treat principle with two-sided type I error with an alpha of 0.05. For participants with missing outcome data, we will perform a sensitivity analysis with missing outcomes excluded or included as an event.

A priori sub-analyses will be performed based on zip code, baseline HbA1c, race, insurance status, and sex with a p-value threshold of 0.1 for these secondary analyses and we will account for multiple testing. A cox proportional hazards model will be performed to assess time-to-prescription between groups.

After the final data was reviewed, a series of subsequent hypotheses were identified for additional analysis. These analyses are, by definition, post hoc and, therefore, considered hypothesis-generating. A p-value of 0.05 will be considered significant without any correction for multiple comparisons.

Interim Analysis

N/A

Quality Control

Data will be collected from our EHR, the MGB Electronic Data Warehouse (EDW), and patients. Clinical laboratories within MGB system have laboratory certificates available upon request.

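### HbA1c and PAM change rest on a paired t-test of observed pairs, and the only committed missing-outcome rule cannot be applied usefully to a continuous outcome

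*SAP*

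**What the plan says.** SAP, Statistical Methods, names the outcomes and the method: "For our co-secondary outcomes, the change in the HbA1c, and PAM from baseline to the end of the 6-month study", and "these will be analysed with a paired t-test and we will report a mean and standard deviation". The same section states "We will conduct our analysis via the intention-to-treat principle with two-sided type I error with an alpha of 0.05". SAP, Definition of Analysis Sets, describes the Full Analysis Set this way: "Patients will be included all patients enrolled (intention-to-treat analysis".

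On missing data the SAP has three statements:

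- Study Sample Size inflates the HbA1c calculation: "To account for dropout, (expecting 25% dropout".
- Data Analysis says "The primary analysis will not impute any missing data", then allows, without committing to it, a sensitivity analysis by last observation carried forward (LOCF).
- Statistical Methods makes the only firm commitment: "we will perform a sensitivity analysis with missing outcomes excluded or included as an event".

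PAM is measured at baseline and end of study only (SAP, Research Question and Objectives). For HbA1c, Protocol, Data and Safety Monitoring, says "HbA1c will be checked at 3 and 6 months after the initiation of therapy".

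**The concern.** A paired t-test needs two values per patient. A patient with no end value drops out of the HbA1c or PAM result, whatever the analysis set is called. The intention-to-treat label therefore promises more than the method delivers.

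The program aims at engagement and drug uptake. Patients who cannot be reached at the end are plausibly those who did not start or keep a drug, or were not activated. If so, the reported mean change flatters the program. A sensitivity analysis should show how far the result depends on those patients, but the one the SAP commits to was written for a yes/no outcome.

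**Working it through.** **Inputs.** From SAP, Study Sample Size: HbA1c SD 1 point, target difference 0.5 points, power 80%, dropout allowance 25%, 100 patients per arm. From SAP, Statistical Methods: two-sided alpha 0.05. The changes in observed and missing patients are my assumptions, because the documents give no outcome data for patients who leave.

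**1. The plan's own figure.** n per arm = 2 × (1.96 + 0.8416)² × 1² / 0.5² = 62.8, so 63. Then 63 / 0.75 = 84. Both match the SAP. This is a between-arm formula, while the paired t-test is a within-group test; that mismatch is a separate matter.

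**2. Size of the loss.** If every dropout also lacks an end value, 100 × 0.25 = 25 are lost per arm. That leaves 75 pairs per arm, or 150 of 200. Two-sample power for 0.5 points is 86.5% at 75 per arm and 94.2% at 100. The problem is bias, not power.

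**3. Size of the bias.** Let m be the missing fraction, c_obs the mean fall in observed patients and c_mis the mean fall in the others.

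- All-enrolled fall = (1 − m) × c_obs + m × c_mis
- Overstatement = m × (c_obs − c_mis)

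| Missing | Fall, observed | Fall, missing | Fall, all enrolled | Overstatement |
|---|---|---|---|---|
| 25% | 0.30 | 0.30 | 0.30 | 0 |
| 25% | 0.30 | 0 | 0.225 | 0.075 |
| 10% | 0.30 | 0 | 0.27 | 0.03 |
| 25% | 0.50 | 0.25 | 0.4375 | 0.0625 |
| 25% | 0.50 | 0 | 0.375 | 0.125 |
| 25% | 0.50 | −0.50 (a rise) | 0.25 | 0.25 |

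In the second row the ratio is 0.30 / 0.225 = 1.33. The same proportion holds for PAM under the same assumption. These are within-group means. In a between-arm difference the bias cancels if both arms lose the same fraction with the same gap in change.

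**4. What each planned safeguard does for a mean change.**

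- Exclusion: the same pairs as the t-test, so nothing new.
- Counting as an event: no event exists, so no value can be entered.
- LOCF: usable. For PAM it equals no change from baseline. For HbA1c it does too, unless an interim value exists. It is optional.
- Linear regression with baseline HbA1c and weight: no missing-data rule is given.
- Longitudinal model: stated for a binary outcome only.

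**5. Would a likelihood model alone repair this?** With baseline and end values only, the model's mean change equals the observed-pairs change minus (1 − b) × (baseline mean of all − baseline mean of observed), where b is the slope of end value on baseline. If missing patients resemble the others at baseline, the second term is zero. The model then returns 0.30, not 0.225. It assumes missing at random, so it cannot be the check on informative dropout.

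**The case against.** The strongest reply is that this is a wording gap in outcomes of lower rank. The primary outcome is untouched, SAP, Exploratory Aim(s), lists HbA1c as exploratory, and the SAP already names LOCF, which for PAM is the no-change analysis. Much of that stands: the gap is between an optional and a committed analysis, not the absence of any usable method.

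Four stronger readings are tempting, and the documents do not support them:

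- *That this is a completer analysis.* The SAP defines completers separately, as the Per Protocol Set. HbA1c can come from the electronic record, withdrawn participants' data are kept, and those who stop the drug are asked about one final contact (Protocol, Research Design and Methods). A leaver may well have an end value. Observed pairs is the accurate term.
- *That improvement is overstated by a third.* The 25% is a dropout allowance, not a known rate of missing HbA1c, and zero change in missing patients is assumed. With equal change there is no bias.
- *That a common 3-month HbA1c is discarded.* No stated SAP analysis uses interim HbA1c. But the Protocol times the tests from the start of therapy, not enrolment. Patients who never start have no such scheduled test, and education-first patients start later by design.
- *That the no-imputation sentence settles the matter.* It may concern only the primary outcome. A paired t-test drops incomplete pairs either way.

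A remedy that fits one common baseline mean to everyone would also be wrong. Patients with baseline HbA1c of 9.0–9.9% go automatically to immediate titration and are outside the A/B comparison (Protocol, Research Design and Methods), so that group's baseline is higher by construction.

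**Conclusion.** The concern holds in this form. HbA1c and PAM change are estimated on observed pairs, under an intention-to-treat label and a 25% dropout allowance, with no committed sensitivity analysis that works for a continuous outcome.

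The overstatement equals the missing fraction times the difference in change. It ranges from 0 to 0.25 HbA1c points over the cases shown, and the largest is half of the 0.5-point target. Its direction is likely, given what the program does, but the documents do not show it. Every figure for missing patients is an assumption. The primary prescription outcome is not affected. The point is worth correcting because the remedy is cheap and can change the reported mean change.

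**What to change.** 1. Restrict the rule that counts missing outcomes as events to the prescription outcome.
2. Commit to a sensitivity analysis for HbA1c and PAM on all enrolled patients with a baseline value. Set missing end values to no change from baseline, and report it beside the main result with the number of missing values by arm. It is not a worst case, since missing patients could have worsened.
3. For the main analysis, use a likelihood-based repeated-measures model with all available values: baseline and end for PAM; baseline, interim and end for HbA1c. Place interim HbA1c by time since enrolment, with stated windows. State that the model assumes missing at random, so step 2 is the check on informative dropout.
4. Apply a common-baseline constraint only to the A/B-allocated patients, and analyse the group with baseline HbA1c of 9.0–9.9% separately.
5. SAP, Statistical Methods, indicates that final data had been reviewed. Date the change and report the new analyses beside the planned paired t-test.

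The cost is SAP wording and a few lines of SAS, with no new patients or data. The estimated improvement may come out slightly less favourable.

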Roughly 50% of patients enrolled into this quality improvement program will be allocated into an “education first” pathway, which will provide 4 weeks of digital, paper, and customized video resources to explain the medical rationale and anticipatory guidance regarding diabetes care and therapeutics with proven benefit prior to becoming eligible for medical therapy prescription. In addition to looking at uptake and adherence, we will be measuring baseline and end-of-study Patient Activation Measures for each participant. Patient Activation Measures have been shown to correlate with increased self-care behaviors, medication adherence, and diabetes monitoring (11).

Primary Aim

The primary objective of this study is to create a remote diabetes management platform that compared to baseline, will improve initiation and adherence to contemporary guidelines regarding the use of glucose-lowering medications with cardiovascular and renal benefit for patients with type 2 diabetes and high cardiovascular and/or renal risk.

Secondary Aim(s)

- Evaluate optimal timing of patient education within the program. (measured as prescriptions by randomization arm, prescriptions at 2 months, and patients on therapy at end of study)
- Increase patient disease knowledge, activation, and engagement (as measured with short-form Patient Activation Measure)

Exploratory Aim(s)

Weight and HbA1c

We will compare age, socioeconomic demographics (where available), baseline characteristics and medical history, HbA1c, and demonstrate that they are evenly distributed in the population and between groups. We will report subgroup-specific rates if there are significant differences (e.g., evidence of heterogeneity).

Data Sources

Data will be collected from the electronic health record (HER) and directly from patients. All data will be stored in an encrypted, secure database within the Mass General Brigham firewall and using HIPAA-compliant applications.

Study Sample Size

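### Read in context, the SAP's secondary regression leaves baseline PAM out of the PAM model, so any between-arm PAM comparison from it is less precise than the collected data allow

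*SAP*

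**What the plan says.** SAP, Statistical Methods, introduces the two continuous outcomes together: "For our co-secondary outcomes, the change in the HbA1c, and PAM from baseline to the end of the 6-month study". It first states that "these will be analysed with a paired t-test and we will report a mean and standard deviation". The next sentence adds the regression: "A secondary analysis will be to conduct linear regression models with two variables (baseline HbA1c and baseline weight) to control for any confounders". That sentence names neither its outcome nor a term for arm.

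Baseline PAM is available. SAP, Research Question and Objectives, says "we will be measuring baseline and end-of-study Patient Activation Measures for each participant", and the protocol (Research Design and Methods) also lists PAM at enrolment and at completion. No section lists baseline PAM as a covariate.

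The only other adjustment rule, also in Statistical Methods, concerns baseline differences between groups: "if any significant differences are found, we will correct for these utilizing logistic regression".

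SAP, Study Sample Size, covers prescriptions and HbA1c. It gives no SD, effect size, power or sample size for PAM.

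**The concern.** One covariate pair serves two different outcomes. For change in HbA1c the pair includes the outcome's own baseline, which is usually the most useful covariate. For change in PAM it does not. A change score is negatively related to its starting value whenever the correlation between the two time points is below 1 (with equal SDs). Leaving the starting value out therefore leaves avoidable variance in the arm contrast. It also leaves in the estimate part of any difference in starting PAM that arises by chance.

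Nothing else in the plan fills the gap. The paired t-test does not compare arms, and logistic regression does not fit a continuous score. Activation is a named secondary aim measured by PAM. The sample size was not set for PAM, so there is no planned reserve of precision.

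**Working it through.** **Inputs from the SAP.** Two-sided alpha 0.05 ("two-sided type I error with an alpha of 0.05"); 100 per arm with 25% dropout, so 100 × 0.75 = 75 evaluable per arm.

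**Assumptions, not in the documents.** The PAM SD is the same at baseline and 6 months, and all PAM results are in units of that SD. The correlation r between the two PAM scores is 0.3 to 0.7, with 0.8 shown as a less favourable case for the point.

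**1. The plan's own continuous-outcome figure.** The only one is for HbA1c: "to obtain 80% power to detect a 0.5% difference in HbA1c, we would need to enroll 63 patients per arm". With SD 1, n = 2 × (1.960 + 0.842)² × 1² / 0.5² = 62.8, which rounds up to 63. With 25% dropout, 63 / 0.75 = 84. Both figures reproduce. Neither concerns PAM, so no stated figure changes below.

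**2. Precision.** Per-patient residual variance is 2(1 − r) for the change score without baseline PAM and 1 − r² with it. The ratio is (1 − r²) / [2(1 − r)] = (1 + r)/2. The equivalent n is 75 divided by this ratio, and the SE inflation is the square root of its inverse. The last column is the power left, without baseline PAM, for an effect that has 80% power with it.

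| r | Variance without | Variance with | Ratio | 75 per arm acts like | SE inflation | Detectable difference at 80% power, without → with (SD) | Power left |
|---|---|---|---|---|---|---|---|
| 0.3 | 1.40 | 0.91 | 0.65 | 115 | 24% | 0.54 → 0.44 | 62% |
| 0.5 | 1.00 | 0.75 | 0.75 | 100 | 15% | 0.46 → 0.40 | 68% |
| 0.7 | 0.60 | 0.51 | 0.85 | 88 | 8% | 0.35 → 0.33 | 73% |
| 0.8 | 0.40 | 0.36 | 0.90 | 83 | 5% | 0.29 → 0.27 | 76% |

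**3. Do the listed covariates make up for it?** A simulation (150 participants, 4,000 runs, r = 0.6) fitted arm, baseline HbA1c and baseline weight, with the two covariates correlated 0 or −0.2 with baseline PAM. The SE of the arm contrast was 0.147 to 0.148 without baseline PAM and 0.131 to 0.133 with it. Under these assumptions the listed pair recovers almost nothing.

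**4. Chance imbalance.** Suppose the arms differ by D at baseline and there is no treatment effect. The expected difference at 6 months is rD. Subtracting D leaves −(1 − r)D in the change-score contrast. For D = 0.2 SD this is −0.14 (r = 0.3), −0.10 (r = 0.5) and −0.06 (r = 0.7). The SE of a chance imbalance at 75 per arm is √(2/75) = 0.163 SD, so 0.2 SD is about 1.2 SE and not unusual. In the simulation the slope of the estimate on the imbalance was about −0.6, −0.4 and −0.2 at r = 0.4, 0.6 and 0.8. It fell to about 0 once baseline PAM was in the model.

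**The case against.** The regression sentence does not say that it applies to PAM. Its two covariates match the exploratory aims, weight and HbA1c, so it could be meant for those outcomes, each with its own baseline. That reading is tenable, but the sentence directly follows the one on the co-secondary outcomes, which favours including PAM. If PAM was not meant, it has no adjusted analysis at all, and the same clarification is needed.

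The first-listed PAM analysis is the paired t-test. The PAM aim is worded as an increase in activation, while the timing aim is measured by prescriptions. A between-arm imbalance does not disturb a pooled within-participant test, and the variance ratio above does not apply to it. This stands: the point concerns only an arm comparison drawn from a secondary model.

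The size rests on an assumed r and equal SDs. This also stands. At r = 0.8 the loss is 10% of variance and 5% of the SE.

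Three stronger readings are tempting, and the documents do not support them:

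- **All of a chance PAM imbalance is carried into the result.** The SAP analyses change, which already subtracts baseline, so only the (1 − r) share remains, with reversed sign.
- **The PAM comparison is biased.** Under random allocation it is unbiased on average. The shift is conditional on a realised imbalance, and the choice is one of efficiency.
- **Missing weights will remove patients from the PAM model.** The protocol text names no weight measurement, but the SAP lists weight as exploratory and draws data from the EHR and patients. Any loss is speculative.

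**Conclusion.** The point holds in limited form. On the natural reading, the linear model for PAM change omits the outcome's own baseline, which is collected, and no other planned analysis supplies that adjustment. Any between-arm PAM estimate from this model has more variance than it needs. Adding baseline PAM would cut that variance by about 35% (r = 0.3) to 15% (r = 0.7), and would remove a conditional shift of about −(1 − r)D from a realised imbalance D.

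These sizes assume equal SDs and an r that the documents do not give. The direction of the precision gain holds for any r below 1 under equal SDs. The paired t-test and every stated sample size and power figure are unaffected. The change should be made, but the study's validity does not depend on it.

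**What to change.** State the outcome, the arm term and the outcome's own baseline for each linear model. For PAM, regress end-of-study PAM on arm and baseline PAM, and report the adjusted mean difference with a 95% CI. Once baseline PAM is in the model, using change or end-of-study score as the outcome gives the same arm estimate. Keep baseline HbA1c for the HbA1c model, and do not require baseline weight in the PAM model. The paired t-test can stay as the within-participant description.

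The cost is a sentence or two in the SAP and no new data collection. The last paragraph of Statistical Methods, in a SAP dated November 16, 2023, indicates that final data had already been reviewed. The change should therefore carry its date and be labelled as made after that review if so. The result of the regression as the SAP now words it should be shown beside it.

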¹ ASCVD for this project is defined as history of myocardial infarction, angina, unstable angina, coronary revascularization, percutaneous coronary intervention, transient ischemic attack (TIA) stroke, peripheral artery disease, carotid artery disease ($> 50\%$ luminal obstruction)

² Hypoglycemia for this project is defined as a blood sugar $< 70 \text{ mg/dL}$

Patients recruited into the program will enter either 1) a gradual education period for 2 months followed by pharmacist and navigator-based medication titration, or 2) rapid education in conjunction with pharmacist and navigator-based medication titration via a Collaborative Drug Therapy Management (CDTM) algorithm designed to improve medical therapy for the treatment of type 2 diabetes with cardiorenal comorbidities. The CDTM will be approved by the BWH Pharmacy and Therapeutics committee. We will use A/B testing to optimize the timing of the educational program. Outcomes will include percentage of patients prescribed SGLT2i or GLP1-RA, percentage of prescriptions filled, HbA1c, change in the diabetes treatment satisfaction questionnaire short (DTSQs) score, and Patient Activation Measure (PAM) at enrollment and completion of the program.

Participants whose HbA1c rises to 9.0-9.9% following enrollment as part of their program baseline labs will automatically be assigned to immediate pharmacist and navigator-based medical titration and rapid education. As a result, participants with baseline HbA1c between 9.0-9.9% will remain in the program but will not be part of the A/B testing.

We will generate prototype software to guide DM medication changes based on patient-specific information and to longitudinally monitor each participant's progress through the algorithm and document

clinical and laboratory information. Basic patient demographic, laboratory, medication, and medical history data will be housed in a secure platform database for clinical management and communication.

Briefly describe study procedures. Include any local site restrictions, for example, “Subjects enrolled at Partners will not participate in the pharmacokinetic portion of the study.” Describe study endpoints.

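### A single Cox hazard ratio from enrolment mixes the scheduled education delay with any effect of education on later prescribing, because the design rules out proportional hazards

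*SAP*

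**What the plan says.** - **The model.** SAP, Statistical Methods: "A cox proportional hazards model will be performed to assess time-to-prescription between groups". No time origin, proportionality check, time-varying term or alternative summary is given.
- **The delayed arm.** SAP, Research Question and Objectives: the education-first pathway is one "which will provide 4 weeks of digital, paper, and customized video resources", all of it "prior to becoming eligible for medical therapy prescription". Protocol, Research Design and Methods, instead describes "a gradual education period for 2 months followed by pharmacist and navigator-based medication titration". The two lengths conflict.
- **The other arm.** Protocol, same section: "rapid education in conjunction with pharmacist and navigator-based medication titration".
- **Follow-up.** The primary outcome runs from baseline to the "conclusion of the study at 6 months post-enrolment" and is tested by chi-square. A cumulative incidence curve is also planned, with no between-arm measure attached to it.
- **The aim served.** SAP, Secondary Aim(s): the best timing of education, measured by prescriptions by arm, "prescriptions at 2 months" and therapy at study end.

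**The concern.** A Cox model with one treatment term assumes that the ratio of the two prescribing rates is the same throughout follow-up. Here the protocolised pathway sets the education-first arm's programme rate to zero for the length of the block and lets it start afterwards. The early ratio is therefore very large by design, and the later ratio is some other number. The fitted value is an average of the two, with weights that depend on block length and prescribing speed.

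This matters because education timing is a stated aim and the Cox model is the SAP's only between-arm time-to-event estimate for it. A ratio above 1 could be taken to show that immediate titration gets more patients onto therapy when it shows only that they start sooner. A ratio near 1 could hide a real benefit of education that has been offset by the delay.

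**Working it through.** **Nearest stated figure.** The SAP gives no hazard ratio, event count or power for the Cox model. Its nearest figure is power above 80% for 5% v 20% with 100 per arm and 25% dropout, so 75 evaluable. Pooled SE = √(2×0.125×0.875/75) = 0.0540; unpooled SE = √((0.05×0.95+0.20×0.80)/75) = 0.0526; (0.15 − 1.96×0.0540)/0.0526 = 0.84, so power is 79.9% (82.7% for the exact power of the chi-square test). The figure reproduces, but it says nothing about the Cox model.

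**Inputs from the documents.** Allocation about 1:1 ("Roughly 50% of patients enrolled into this quality improvement program will be allocated" to education-first); 6 months from enrolment; block b = 2 months, or 4 weeks (4/4.345 = 0.92 month); 20% intervention uptake and 5% secular uptake (SAP, Study Sample Size).

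**Assumptions.** Uptake is identical in both arms once patients are eligible, so education has no effect. Prescribing is either *fast* (spread evenly over the 2 months after eligibility) or at a *constant hazard*. The 50% uptake is an added range value; the SAP gives only 20%.

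**Method.** The large-sample hazard ratio θ (immediate v education-first) solves the Cox score equation ∫ f_I − (f_I+f_E)·θS_I/(θS_I+S_E) dt = 0 over 0–6 months, where I is the immediate arm and E the education-first arm.

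| Uptake once eligible | Block | 6-month uptake, immediate v education-first | Hazard ratio |
|---|---|---|---|
| 20%, fast | 4 weeks | 20% v 20% | 1.08 |
| 20%, fast | 2 months | 20% v 20% | 1.12 |
| 20%, constant hazard | 4 weeks | 20% v 17.2% | 1.20 |
| 20%, constant hazard | 2 months | 20% v 13.8% | 1.55 |
| 50%, fast | 4 weeks | 50% v 50% | 1.28 |
| 50%, fast | 2 months | 50% v 50% | 1.41 |

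**Hand checks.**
- *Fast, 2-month block.* All immediate-arm events fall in months 0–2, while S_E = 1. All education-first events fall in months 2–4, while S_I = 1−p. The equation then solves exactly to θ = 1/√(1−p): 1/√0.8 = 1.12 and 1/√0.5 = 1.41.
- *Constant hazard.* λ = −ln(0.8)/6 = 0.0372 per month. Education-first uptake is 1 − 0.8^(4/6) = 13.8% or 1 − 0.8^(5.08/6) = 17.2%. With few events θ is close to the ratio of cumulative hazards, 6/(6−b): 6/4 = 1.50 and 6/5.08 = 1.18.

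**Outside prescribing during the block.** At the SAP's 5% per 6 months the block hazard is −ln(0.95)/6 = 0.0085, and 0.0085/0.0372 = 0.23. The ratio of immediate to education-first is then 1/0.23 = 4.3 within the block and 1 after it. The 6-month value becomes 1/0.871 = 1.15 (4 weeks) or 1/0.727 = 1.38 (2 months).

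**If education does change later uptake.** Take 20% uptake, a constant hazard and a 2-month block, and let education raise the later hazard by half. The cumulative hazard is 1.5λ×4 = 6λ, so both arms reach 20%. The Cox value is 1/0.963 = 1.04, and a real 50% gain all but disappears. Letting education multiply the later hazard by 0.5 to 2 moves the 6-month ratio from 1/0.419 = 2.39 to 1/1.655 = 0.60 (4 weeks), or from 1/0.327 = 3.06 to 1/1.276 = 0.78 (2 months).

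**Restricted mean.** With fast prescribing, the area between two curves shifted by b is p×b. For a 2-month block this is 0.20×2 = 0.4 month or 0.50×2 = 1.0 month.

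**The case against.** The strongest reply is that the model is meant to assess time to prescription, and an education-first strategy does lengthen that time. Detecting the delay is then a correct answer. This stands. A reader might infer that the hazard ratio is a pure artefact, or that a significant result would be a false positive. The documents support neither, because the SAP never says that it wants the hazard after eligibility, and education may change later uptake. With a constant hazard and a 2-month block, 6-month uptake itself differs (20% v 13.8%), and in simulation the chi-square test rejects about as often as Cox (23% v 26%).

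The restricted mean does not remove the delay either. At 50% uptake with fast prescribing and a 2-month block, its test rejects in about 92% of simulated trials of 100 per arm, against 40% to 43% for Cox. The case for it is interpretability, not protection against rejection.

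Other points also stand:
- Treating physicians can prescribe during the block, so the rate may be small rather than zero. The ratio still changes from 4.3 to 1.
- At the SAP's 20% with fast prescribing the distortion is small (about 1.1, about 6% rejection).
- No Cox analysis before 6 months is planned, so the larger ratios that earlier cut-offs would give are not at issue.
- The cumulative incidence curve would show the delay, but it supplies no estimate.

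**Conclusion.** The point holds, provided the clock starts at enrolment. Proportional hazards is contradicted by the allocation itself, and the single 6-month ratio has no fixed meaning for choosing when to educate. With no effect of education it ranges from about 1.1 to 1.55 across the cases above, depending on block length, uptake and prescribing speed. With a real effect it can fall near 1 or below. These sizes rest on the assumed uptake patterns; the non-proportionality does not.

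The consequence is limited to a supportive analysis. The primary chi-square test needs no proportional hazards and is unaffected. A ratio above 1 would reflect a real delay, but it could not by itself show greater eventual uptake. The change is worth making before the timing results are interpreted. The same caution applies to the 2-month comparison: under a 2-month block, its education-first count can contain only outside prescriptions.

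**What to change.** 1. State that time to first prescription is counted from enrolment in both arms, and reconcile the block length between the SAP and the protocol.
2. Replace the single hazard ratio as the summary with the difference in restricted mean time to first prescription over 0–6 months, with a 95% CI. Present it beside the cumulative incidence curve and the 6-month proportions, and describe it as including the designed delay.
3. If a hazard ratio is kept, report it separately for the block and after it, or start the clock at the date of eligibility with equal post-eligibility follow-up in both arms. In simulation with identical uptake once eligible, the eligibility clock rejects in 4.9% to 5.3% of trials.

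**Cost.** A few SAP sentences and a few lines of SAS, with no new data beyond a recorded eligibility date. Both versions of the hazard ratio use fewer events. The split version compares patients still unprescribed at the end of the block, by which time the immediate arm may have used up its willing patients. The eligibility version drops patients lost or prescribed during the block. Since the SAP already refers to review of the final data, the amendment should be dated and should give the design, not the results, as its reason.
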